3. ENDPOINTS AND BASELINE VARIABLES: DEFINITIONS AND CONVENTIONS

[Appendix 1](#) shows how the study estimands and endpoints relate to each objective. [Section 6](#) describes the planned analyses and summaries.

3.1. Primary Endpoints

3.1.1. Primary Immunogenicity Endpoints

- hSBA titer for each of the MenACWY test strains.
- hSBA titer for each of the primary MenB test strains (A22, A56, B24, and B44).

3.1.2. Primary Safety Endpoints

- Local reactions (pain, redness, and swelling).
- Systemic events (fever, vomiting, diarrhea, headache, fatigue, chills, muscle pain other than muscle pain at any injection site, and joint pain).
- Use of antipyretic medications within 7 days after each vaccination visit.
- AEs, SAEs, MAEs, NDCMCs, and immediate AEs.
- Days missing from school or work because of AEs.

3.2. Secondary Endpoints

3.2.1. Secondary Immunogenicity Endpoints

- hSBA titer for each of the MenACWY test strains.

3.3. Tertiary/Exploratory Endpoints

- hSBA titer for each of the MenACWY test strains.
- hSBA titer for each of the primary MenB test strains (A22, A56, B24, and B44).
- hSBA titer for each of the secondary MenB test strains.

The tertiary/exploratory immunogenicity endpoint related to secondary MenB test strains induced by 2 doses of MenABCWY will be reported if requested/required.

3.4. Baseline Variables

3.4.1. Demographic, Medical History, and Baseline Characteristic Variables

Demographic variables collected at Visit 1 include sex, race, ethnicity, and date of birth. Race collected includes:

- Black or African American
- American Indian or Alaska Native
- Asian
- Native Hawaiian or other Pacific Islander
- White
- Not reported

Ethnicity collected includes:

- Hispanic or Latino
- Non-Hispanic/non-Latino
- Not reported

Age at the time of first vaccination and age at randomization will be derived based on birthday. For example, if the first vaccination date is 1 day before the participant's 13th birthday, the participant is 12 years old.

Medical history will be assessed at Visit 1 and categorized according to the current version (at the time of reporting) of MedDRA.

Physical examination will be assessed prior to vaccination at Visit 1 and each body system examined will be recorded in the CRF as normal, abnormal, or not done.

3.4.2. Previous Vaccinations

For participants who have ever received a PRP-OMP vaccine, the name of the vaccine and date of administration will be recorded on the CRF.

Similarly, for participants who have received any prior meningococcal vaccines or vaccines containing 1 or more MenACWY groups, the trade name and date of administration will be recorded on the CRF.

3.5. Safety Endpoints

3.5.1. Adverse Events

A 3-tier approach will be used to summarize AEs. Under this approach, AEs are classified into 1 of 3 tiers. Different analyses will be performed for different tiers (see [Section 6.6.1](#)).

Tier 1 events: These are prespecified events of clinical importance. There is no Tier 1 event identified for MenABCWY at this stage.

Tier 2 events: These are events that are not Tier 1 but are “relatively common.” A MedDRA PT is defined as a Tier 2 event if there are at least 4 participants in at least 1 combined group reporting the event.

Tier 3 events: These are events that are neither Tier 1 nor Tier 2 events.

The relationship between (S)AEs and the investigational products will be characterized as related or not related as determined by investigators and as described in the protocol. The severity of AEs will be characterized as mild, moderate, and severe.

The time period for actively eliciting and collecting (S)AEs, MAEs, and NDCMCs for each participant is outlined in Table 4.

Table 4. Summary of Adverse Event Collection

	Visits 1-4	Visit 5
Approximate Month	0-7	12
Nonserious AEs	ICD through and including Visit 4 (1 month after Vaccination 2)	
SAEs	ICD through and including Visit 4 (1 month after Vaccination 2)	Since Visit 4
MAEs	ICD through and including Visit 4 (1 month after Vaccination 2)	Since Visit 4
NDCMCs	ICD through and including Visit 4 (1 month after Vaccination 2)	Since Visit 4

Abbreviations: ICD = informed consent document; MAE = medically attended adverse event; NDCMC = newly diagnosed chronic medical condition.

An MAE is defined as a nonserious AE that results in an evaluation at a medical facility, and participants who missed days of school or work because of an AE will be captured via the AE checklist (See [Table 3](#)). Neuroinflammatory and autoimmune conditions will also be captured via the AE checklist. An NDCMC is defined as a disease or medical condition not previously identified that is expected to be persistent or otherwise long-lasting in its effects.

The time period for actively eliciting and collecting AEs and SAEs (“active collection period”) for each participant/parent(s)/legal guardian begins from the time the participant provides informed consent, which is obtained before the participant’s participation in the study (ie, before undergoing any study-related procedure and/or receiving investigational product), through and including Visit 4. At Visit 5, the participant will be contacted by telephone to inquire about SAEs, MAEs, and NDCMCs since Visit 4.

For participants who are screen failures, the active collection period ends when screen failure status is determined.

Medical occurrences that begin before the start of investigational product administration but after obtaining informed consent will be recorded on the Medical History/Current Medical Conditions section of the CRF, not the AE section.

All events collected on the CRF will be categorized according to the current version (at the time of reporting) of MedDRA.

3.5.1.1. Analysis Intervals

There will be 6 analysis intervals for the AE data collected via the CRF (Table 5). The analysis populations used for these intervals are described in detail in [Section 4](#).

Table 5. Analysis Intervals for AEs, SAEs, MAEs, NDCMCs, and Days Missing School or Work Because of AEs

#	Analysis Interval	Analysis Population	Interval Start Date (Inclusive)	Interval Stop Date (Inclusive)	Safety Data
1	Within 30 days after Vaccination 1	Vaccination 1 safety	Vax 1 date	Vax 1 date + 30 days	AEs, SAEs, MAEs, NDCMCs
2	Within 30 days after Vaccination 2	Vaccination 2 safety	Vax 2 date	Vax 2 date + 30 days	AEs, SAEs, MAEs, NDCMCs
3	Within 30 days after any vaccination	Safety	Vax 1 date or Vax 2 date	Vax 1 date + 30 days or Vax 2 date + 30 days	AEs, SAEs, MAEs, NDCMCs
4	During vaccination phase	Safety	Visit 1 date	Visit 4 date (or end of vaccination day)	AEs, SAEs, MAEs, NDCMCs, days missing school or work because of AEs
5	During follow-up phase	Follow-up safety	Visit 4 date + 1, or end of vaccination date + 1 for early-withdrawal participants	Visit 5 date	SAEs, MAEs, NDCMCs
6	Throughout study	Safety	Visit 1 date	Visit 5 date	SAEs, MAEs, NDCMCs

Abbreviations: MAE = medically attended adverse event; NDCMC = newly diagnosed chronic medical condition.

Two analysis intervals will be applied to immediate AEs (Table 6).

Table 6. Analysis Intervals for Immediate AEs

#	Analysis Interval	Analysis Population	Interval Start Date/Time (Inclusive)	Interval Stop Date/Time (Inclusive)
1	Vaccination 1	Vaccination 1 safety	Vax 1 time	Vax 1 time + 30 minutes
2	Vaccination 2	Vaccination 2 safety	Vax 2 time	Vax 2 time + 30 minutes

3.5.2. Reactogenicity Data

Reactogenicity data are solicited AEs. The reactogenicity data collected from the study e-diary will include: local reactions (redness, swelling, and pain at the injection site) and systemic events (fever, vomiting, diarrhea, headache, fatigue, chills, muscle pain other than muscle pain at the injection site, and joint pain), and use of antipyretic medication.

The e-diary will record reactogenicity data from Day 1 to Day 7 starting on the day of each vaccination (Day 1), following investigational product administration. Local reactions at the site of investigational product administration only on the left arm will be recorded.

Three analysis intervals will be applied to reactogenicity data (Table 7).

Table 7. Analysis Interval for Reactogenicity Data

#	Analysis Interval	Analysis Population	Interval Start Date (Inclusive)	Interval Stop Date (Inclusive)
1	Vaccination 1	Vaccination 1 safety	Vax 1 date	Vax 1 date + 6 days (or until resolved day)
2	Vaccination 2	Vaccination 2 safety	Vax 2 date	Vax 2 date + 6 days (or until resolved day)
3	Any vaccination	Safety	Vax 1 or Vax 2 date	Vax 1 or Vax 2 + 6 days (or until resolved day)

3.5.2.1. Local Reactions Endpoints

For each local reaction, the derivation of whether or not the specific reaction occurred on each day and “any day (Days 1-7)” will be made. The variable will be calculated for each vaccination as well as overall reactions for any vaccination. The derivation of this variable is given in [Table 8](#).

Table 8. Derived Variables for Local Reactions

Variable	Yes (1) ^a	No (0) ^b	Missing (.)
Each day (Days 1-7)	Participant/parent/legal guardian reports the reaction as “mild,” “moderate,” or “severe” on each individual day.	Participant/parent/legal guardian reports the reaction as “none” on the individual day.	Participant did not report on the reaction on the individual day.
Any day (Days 1-7)	Participant/parent/legal guardian reports the reaction as “mild,” “moderate,” or “severe” on any day (Days 1-7).	Participant/parent legal guardian reports the reaction as “none” on all 7 days or as a combination of “none” and missing on all 7 days.	Participant did not report on the reaction on any of the 7 days.

- a. For redness and swelling, “mild,” “moderate, and “severe” categories are based on the caliper size reported from the e-diary and defined in Table 9.
- b. For redness and swelling, “none” means 0 to 4 caliper units reported in the e-diary.

A caliper (measuring device) is used to measure the redness or swelling of the injection site area. Caliper units (range: 1-21+) are converted to centimeters according to 1 caliper unit = 0.5 centimeters and then categorized as none, mild, moderate, or severe based on the grading scale of local reactions in Table 9. Pain at the injection site will be assessed by the participant/parent/legal guardian according to the grading scale in Table 10.

Table 9. Grading of Redness and Swelling

None	0 to 2.0 cm (0 to 4 caliper units)
Mild	>2.0 to 5.0 cm (5 to 10 caliper units)
Moderate	>5.0 to 10.0 cm (11 to 20 caliper units)
Severe	>10.0 cm (>20 caliper units)

Table 10. Grading of Pain at Injection Site

None	No pain
Mild	Does not interfere with activity
Moderate	Interferes with activity
Severe	Prevents daily activity

The maximum severity (highest grading) of each local reaction within 7 days after vaccination will be derived for each vaccination as well as any vaccination. The maximum severity will be derived as follows:

- = ●, if values are missing for all days (Days 1-7);
- = 0, if the participant/parent/legal guardian reports all reactions as “none” or a combination of missing and “none” for all days (Days 1-7);
- = *highest grade* (maximum severity) within 7 days after vaccination, if the answer is not “none” for at least 1 day.

For participants experiencing any local reactions (or those with derived reaction presence in [Table 8](#)), the maximum duration (last day of reaction - first day of reaction + 1) will be derived for the study vaccination. Resolution of the event is the last day on which the event is recorded in the e-diary or the date the event ends if it is unresolved during the participant diary-recording period (end date collected on the CRF), unless chronicity is established. If there is no known end date, the duration will be considered unknown and set to missing.

For reactions that continue into the next vaccination visit, the duration will be calculated in a segmented fashion. The reaction end date will be set to the day prior to the next vaccination and will have a new start date as the day of next vaccination and duration will be calculated separately from this start date to the date of resolution. Participants with reactions spanning multiple vaccination visits will be included in a footnote.

Participants with no reported reaction have no duration.

In summary, the following variables will be derived for local reactions:

1. Each local reaction on each day (Days 1-7) after each vaccination.
2. Each local reaction on any day (Days 1-7) after each vaccination and any vaccination.
3. Any local reaction on any day (Days 1-7) after each vaccination and after any vaccination.
4. Maximum severity of each local reaction on any day (Days 1-7) after each vaccination and any vaccination.
5. Maximum duration of each local reaction after each vaccination.

3.5.2.2. Systemic Events Endpoints

Participants will be asked to assess the severity of each event according to [Table 11](#).

Table 11. Grading of Systemic Events

	Grade 1 (Mild)	Grade 2 (Moderate)	Grade 3 (Severe)
Vomiting	1 to 2 times in 24 hours	>2 times in 24 hours	Requires IV hydration
Diarrhea	2 to 3 loose stools in 24 hours	4 to 5 loose stools in 24 hours	6 or more loose stools in 24 hours
Headache	Does not interfere with activity	Some interference with activity	Prevents daily routine activity
Fatigue	Does not interfere with activity	Some interference with activity	Prevents daily routine activity
Chills	Does not interfere with activity	Some interference with activity	Prevents daily routine activity
Muscle pain (other than muscle pain at the injection site)	Does not interfere with activity	Some interference with activity	Prevents daily routine activity
Joint pain	Does not interfere with activity	Some interference with activity	Prevents daily routine activity

Abbreviation: IV = intravenous.

Oral temperature will be collected in the e-diary, daily, for 7 days after each vaccination and at any time during the 7 days when fever is suspected. The highest temperature for each day will be recorded in the e-diary. The protocol defines fever as an oral temperature $\geq 38.0^{\circ}\text{C}$ ($\geq 100.4^{\circ}\text{F}$). Fever will be scaled as shown in Table 12.

Table 12. Severity Scale for Fever

Temperature 38.0°C to 38.4°C
Temperature $>38.4^{\circ}\text{C}$ to 38.9°C
Temperature $>38.9^{\circ}\text{C}$ to 40.0°C
Temperature $>40.0^{\circ}\text{C}$

For each systemic event, the following variables will be available, similar to local reactions:

1. Each systemic event on each day (Days 1-7) after each vaccination.
2. Each systemic event on any day (Days 1-7) after each vaccination and any vaccination.
3. Any systemic event on any day (Days 1-7) after each vaccination and after any vaccination.
4. Maximum severity of each systemic event on any day (Days 1-7) after each vaccination and any vaccination.
5. Maximum duration of each systemic event after each vaccination.

The derivation of these variables is similar to the derivation of the variables for local reactions ([Section 3.5.2.1](#)).

3.5.2.3. Use of Antipyretic Medication

The use of antipyretic medication will be recorded in the e-diary for 7 days (Day 1 to Day 7) after each vaccination.

The following variables will be derived:

1. Use of antipyretic medication on each day (Days 1-7) after each vaccination.
2. Use of antipyretic medication on any day (Days 1-7) after each vaccination and any vaccination.
3. Maximum duration of use of antipyretic medication after each vaccination.

3.5.3. Pregnancy Testing

The results of the urine pregnancy tests collected at Visits 1 and 3 will be recorded.

3.5.4. Laboratory Data

Laboratory assessments will not be collected for this study.

3.5.5. Medical Device Errors

Medical device incidents or malfunctions of the device that result in an incident will be detected, documented, and reported during all periods of the study in which the medical device is used. If a medical device error involves an AE, it will be summarized according to AE reporting conventions.

3.6. Study Conduct

3.6.1. E-Diary Completion

For any given day, an e-diary will be transmitted and considered complete if all expected data (the 3 local reactions, the 9 systemic events including fever, and the use of antipyretic medications) are available. If all data are missing for all items on the e-diary, for all days following vaccination, the e-diary will be considered not transmitted. An e-diary will be considered completed if all expected data for all days are available (ie, not missing) and data are valid. Otherwise, the e-diary will be considered incomplete. For any given day, an e-diary will be considered complete if all expected data are available.

The following e-diary compliance variables will be provided for each vaccination:

1. Compliance per day: the numerator is the number of participants who completed (transmitted) the e-diary on a given day (Day 1 to Day 7) and the denominator is the total number of participants who received the vaccination.

2. At least X days: the numerator is the number of participants who completed (transmitted) the e-diary on X days and the denominator is the total number of participants who received a vaccination (X = 1 through 7; compliance will be computed for each value of X).
3. All 7 days: the numerator is the number of participants who completed (transmitted) the e-diary on all 7 days and the denominator is the total number of participants who received a vaccination.

3.6.2. Nonstudy Vaccines and Concomitant Medications

The name and date of administration of any nonstudy vaccine (or allergen immunotherapy) given from the signing of the ICD up to Visit 4 will be recorded on the CRF.

Permitted during the study include:

Nonstudy vaccines used in the event of a disease outbreak or pandemic are allowed. However, while prioritizing standard clinical care, efforts should be made not to administer nonstudy vaccines within 14 days (for nonlive vaccines) or 28 days (for live vaccines) as specified below (see exception below for any COVID-19 vaccination). Guidance provided by the CDC states that COVID-19 vaccines and other vaccines may now be administered without regard to timing. Because of the COVID-19 pandemic and the ongoing COVID-19 vaccinations at the time of study recruitment, participants will be allowed to receive any authorized (nonexperimental) COVID-19 vaccination within 8 days of investigational product administration (ie, not permitted 7 days before or after any study vaccination).

- Nonstudy vaccines (other than any meningococcal vaccines) that are part of recommended immunization schedules are allowed anytime during the study but should not be administered within 14 days (for nonlive vaccines) and 28 days (for live vaccines) of investigational product administration.
- Antipyretic and other pain medication to treat symptoms following investigational product administration is permitted.
- A local anesthetic may be used at the site of the blood draw.
- Topical antibiotics are permitted.
- Topical and inhaled corticosteroids are permitted.

The name, start and stop dates, and route of administration for concomitant medications (prescription and nonprescription) used to treat an AE (excluding events recorded only in the e-diary) from the signing of the ICD through Visit 5 will be recorded in the CRF.

Treatments will be categories according to the current version (at the time of reporting) of the WHO Drug Dictionary.

4. ANALYSIS SETS (POPULATIONS FOR ANALYSIS)

Data for all participants will be assessed to determine if participants meet the criteria for inclusion in each analysis population prior to unblinding and releasing the database and classifications will be documented per standard operating procedures.

Population	Description
Enrolled	All participants who sign the ICD.
Randomly assigned to investigational product (as randomized), also termed the ITT population	All participants who are assigned a randomization number in the IRT system.
Evaluable	Defined according to post-Vaccination 1 evaluable and post-Vaccination 2 evaluable criteria.
mITT	All participants who received at least 1 study vaccination and have at least 1 valid and determinate MenB or MenACWY assay result available at any time point from Visit 1 to Visit 4.
Safety	All randomized participants who receive at least 1 dose of the investigational product and have safety data reported after vaccination. Participants will be analyzed according to the vaccine they actually received.

Defined Population for Analysis	Description
Post-Vaccination 1 evaluable immunogenicity population	
 1. Were randomized to the study group of interest. 2. Were eligible through Visit 2, ie, fulfilling all of the inclusion criteria and none of the exclusion criteria at each visit where eligibility criteria are collected and confirmed. 3. Received the investigational products at Visit 1 as randomized. 4. Had blood drawn for assay testing within the required time frames at Months 0 (Visit 1: before Vaccination 1) and - (Visit 2: 1 month after the first vaccination: window 28-49 days). 5. Had at least 1 valid and determinate MenACWY assay result at Visit 2. 6. Had received no prohibited vaccines or treatment through Visit 2. 7. Had no important protocol deviations through Visit 2.
Post-Vaccination 2 evaluable immunogenicity population	
 1. Were randomized to the study group of interest. 2. Were eligible through Visit 4, ie, fulfilling all of the inclusion criteria and none of the exclusion criteria at each visit where eligibility criteria are collected and confirmed. 3. Received the investigational products at Visit 1 and Visit 3 as randomized. 4. Had blood drawn for assay testing within the required time frames at Months 0 (Visit 1: before Vaccination 1) and 7 (Visit 4: 1 month after the second vaccination: window 28-49 days). 5. Had at least 1 valid and determinate MenACWY or MenB assay result at Visit 4. 6. Had received no prohibited vaccines or treatment through Visit 4. 7. Had no important protocol deviations through Visit 4.

Defined Population for Analysis	Description
Vaccination 1 safety population	This population will include participants who received the first dose of investigational product at Visit 1 and for whom safety information is available from Visit 1 to prior to Visit 3.
Vaccination 2 safety population	This population will include participants who received the second dose of investigational product at Visit 3 and for whom safety information is available from Visit 3 to Visit 4.
Follow-up safety population	This population will include participants who received at least 1 dose of investigational product and for whom safety information is available from after Visit 4 through Visit 5.

For determination of the evaluable immunogenicity population(s), items 1 through 5 will be computerized checks of the data, while items 6 and 7 will be determined by clinical review. A major protocol violation is a protocol violation that, in the opinion of the sponsor's global medical monitor, would materially affect assessment of immunogenicity, eg, participant receipt of a prohibited vaccine or medication that might affect immune response or a medication error with suspected decrease in potency of the vaccine. The global medical monitor from the sponsor will identify those participants with a protocol violation prior to unblinding of the study.

Participants withdrawn early will be included in the follow-up safety population, in case they have any type of AEs in the AE follow-up interval.

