9.1. Estimands and Statistical Hypotheses

9.1.1. Estimands

The estimands corresponding to each primary, secondary, and tertiary/exploratory objective are described in the table in [Section 3](#). For estimands to evaluate the immunogenicity objectives for noninferiority, these estimands estimate the vaccine effect in the hypothetical setting where participants follow the study schedules and protocol requirements as directed. This addresses the objective of estimating the maximum potential difference between 2 groups, since the impact of noncompliance is likely to diminish the observed difference between the 2 groups. The mechanism for missing data is assumed to be missing completely at random (MCAR), and missing serology results will not be imputed.

In the primary safety objective evaluations, missing e-diary data will not be imputed. Missing AE dates will be imputed according to Pfizer safety rules.

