9.3. Populations for Analysis

For purposes of analysis, the following populations are defined:

Population	Description
Enrolled	All participants who sign the ICD.
Randomly assigned to investigational product	All participants who are assigned a randomization number in the IRT system.
Evaluable	Defined according to post-Vaccination 1 evaluable and post-Vaccination 2 evaluable criteria.
Modified intent-to-treat	All participants who received at least 1 study vaccination and have at least 1 valid and determinate MenB or MenA/C/W/Y assay result available at any time point from Visit 1 to Visit 4.
Safety	All randomized participants who receive at least 1 dose of the investigational product and have safety data reported after vaccination. Participants will be analyzed according to the vaccine they actually received.

Defined Population for Analysis	Description
Post-Vaccination 1 evaluable	All randomized participants who were eligible throughout Visit 2, received the investigational products at Visit 1 as randomized, had blood drawn for assay testing within the required time frames at Months 0 (Visit 1: before Vaccination 1) and 2 (Visit 2: 1 month after the first vaccination: window 28-42 days), had at least 1 valid and determinate MenA/C/W/Y assay result at Visit 2, had received no prohibited vaccines or treatment through Visit 2, and had no important protocol deviations through Visit 2. An important protocol deviation is a protocol deviation that, in the opinion of the sponsor's global medical monitor, would materially affect assessment of immunogenicity, eg, participant receipt of a prohibited vaccine or medication that might affect immune response or a medication error with suspected decrease in potency of the vaccine.

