Post-Vaccination 2 evaluable	All randomized participants who were eligible throughout Visit 4, received the investigational products at Visit 1 and Visit 3 as randomized, had blood drawn for assay testing within the required time frames at Months 0 (Visit 1: before Vaccination 1) and 7 (Visit 4: 1 month after the second vaccination: window 28-42 days), had at least 1 valid and determinate MenA/C/W/Y or MenB assay result at Visit 4, had received no prohibited vaccines or treatment through Visit 4, and had no important protocol deviations through Visit 4. An important protocol deviation is a protocol deviation that, in the opinion of the sponsor's global medical monitor, would materially affect assessment of immunogenicity, eg, participant receipt of a prohibited vaccine or medication that might affect immune response or a medication error with suspected decrease in potency of the vaccine.

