9.4.1. Immunogenicity Analyses

Primary	
For each of the 4 ACWY test strains, the difference in the percentages of seroresponders, defined as participants achieving a 4-fold rise from baseline, in Group 1 at 1 month after Vaccination 2 compared to Group 2 at 1 month after Vaccination 1, and also the difference in seroresponders in Group 3 at 1 month after Vaccination 2 compared to Group 4 at 1 month after Vaccination 1, will be calculated.
 
For each of the 4 primary MenB test strains, the differences of the 4-fold rises and composite responses of Groups 1 and 3 combined compared to Groups 2 and 4 combined at 1 month after Vaccination 2 will be calculated.
 
The Miettinen and Nurminen method will be used to derive the CI for the difference in percentages between vaccine groups. The lower limit of the CI will be used in the hypothesis test for noninferiority as detailed in Section 9.1.
 
The analysis for the ACWY test strains is based on the post-Vaccination 1 evaluable population for Groups 2 and 4 and on the post-Vaccination 2 evaluable population for Groups 1 and 3 and the analysis for the primary MenB strains is based on the post-Vaccination 2 evaluable population in order to provide a comparison that has the greatest chance of identifying a difference between the groups with respect to immunogenicity, if a meaningful difference in vaccine effect actually exists.
 
Exact 2-sided 95% CIs for the percentages (seroresponders, 4-fold-rises and composite responses) will be provided using the Clopper-Pearson method.
 
A supportive analysis will be performed based on the modified intent-to-treat (mITT) population. Participants will be summarized according to the vaccine group to which they were randomized. Missing serology data will not be imputed.

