3/ 13 Jul 2022	Amendment 2 13 Jun 2022	
Modifications in the definitions of the immunogenicity analysis populations.
 
Administrative changes to be consistent with protocol amendment 2.
	
 Extended the window for the post-Vaccination 1 blood draw visit (Visit 2) and the post-Vaccination 2 blood draw visit (Visit 4) to “28 to 49 days” after the previous vaccination visit in the definitions of the post-Vaccination 1 evaluable immunogenicity population and the post-Vaccination 2 evaluable immunogenicity population in Section 4. Moved secondary MenB strain immunogenicity objectives from secondary immunogenicity objectives to tertiary/exploratory objectives.

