2.1.4. Primary Estimands

- **Primary Immunogenicity Estimands**

For the primary, secondary, and exploratory estimands below, ACWY-experienced is defined as receiving a US-licensed MenACWY vaccine at least 4 years prior to enrollment.

For the primary estimands to demonstrate the immunogenicity objectives for noninferiority, the estimands estimate the vaccine effect in the hypothetical setting where participants follow the study schedules and protocol requirements as directed. This addresses the objective of estimating the maximum potential difference between 2 groups, since the impact of noncompliance is likely to diminish the observed difference between the 2 groups.

For the first primary objective (to demonstrate that the immune response for MenA, MenC, MenW, and MenY induced by 2 doses of MenABCWY is noninferior to the immune response induced by 1 dose of MenACWY-CRM, for ACWY-naïve and ACWY-experienced participants separately), there are 2 primary estimands with the following attributes (ACWY-naïve and ACWY-experienced participants separately):

For ACWY-naïve participants:

- Population: ACWY-naïve participants receiving at least 1 dose (Group 2) of MenACWY-CRM or 2 doses (Group 1) of MenABCWY and who are in compliance with the key protocol criteria (evaluable participants).
- Variable: hSBA titer for each of the MenACWY test strains (MenA, MenC, MenW, and MenY).
- Intercurrent event(s): Participants will be summarized according to the vaccine group to which they were randomized. Missing serology data will not be imputed.
- Population-level summary: Difference in the percentage of seroresponders, defined as participants achieving at least a 4-fold rise in hSBA titer from baseline for each MenACWY test strain, 1 month after Vaccination 2 in Group 1 compared to 1 month after Vaccination 1 in Group 2.

- For participants with a baseline hSBA titer below the LOD (or an hSBA titer of <1:4), a 4-fold response is defined as an hSBA titer of $\geq 1:16$.
- For participants with a baseline hSBA titer of \geq LOD (ie, hSBA titer of $\geq 1:4$) and < LLOQ (ie, hSBA titer of 1:8), a 4-fold response is defined as an hSBA titer of ≥ 4 times LLOQ.
- For participants with a baseline hSBA titer of \geq LLOQ, a 4-fold response is defined as an hSBA titer of ≥ 4 times the baseline titer.

For ACWY-experienced participants:

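### Does the SAP's 28-49 day blood-draw window, against 28-42 days in the protocol, weaken the primary noninferiority analysis?

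*SAP*

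**What the plan says.** The two documents give different windows for the same populations.

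- Protocol 9.3, post-Vaccination 1 evaluable: "Visit 2: 1 month after the first vaccination: window 28-42 days". Post-Vaccination 2 evaluable: "Visit 4: 1 month after the second vaccination: window 28-42 days".
- SAP section 4, post-Vaccination 1 evaluable: "Visit 2: 1 month after the first vaccination: window 28-49 days". Post-Vaccination 2 evaluable: "Visit 4: 1 month after the second vaccination: window 28-49 days".

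The visit schedules (Protocol 1.3 and SAP 2.3, Table 3) both keep 28 to 42 days. The SAP version history, version 3, shows that the change was deliberate. Its entry begins "Extended the window for the post-Vaccination 1 blood draw visit (Visit 2) and the post-Vaccination 2 blood draw visit (Visit 4" and goes on to the new range of 28 to 49 days. The rationale column says only that the population definitions were modified.

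These sets carry every primary noninferiority test (SAP 6.1.1.1 to 6.1.1.3). On the estimand, SAP 2.1.4 says that "the estimands estimate the vaccine effect in the hypothetical setting where participants follow the study schedules and protocol requirements as directed". The supportive population, mITT, has no draw window. It is analysed unconditionally for the ACWY endpoints, but for MenB only if it differs from the evaluable set by more than 10% (SAP 6.1.1.3.2).

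**The concern.** The primary set now takes in draws that are off schedule by the plan's own visit table, although the estimand is framed around participants who keep to the schedule. Protocol 9.1.1 prefers compliant participants "since the impact of noncompliance is likely to diminish the observed difference between the 2 groups", and Protocol 9.4.1 says the evaluable sets were chosen "in order to provide a comparison that has the greatest chance of identifying a difference between the groups with respect to immunogenicity". On that reasoning, admitting late draws would shrink a real deficit and make noninferiority easier to declare.

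In the ACWY comparisons the arms are also sampled at different visits (Visit 4 for MenABCWY, Visit 2 for MenACWY-CRM), so the share of late draws need not be equal. No planned inferential analysis goes back to days 28-42. If the effect were material, a product could pass a margin that it would have missed under the protocol's window.

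**Working it through.** **1. The plan's own power figure.** Protocol 9.2.1 multiplies the power for its three components: 0.9993 × 0.9945 × 0.9163 = 0.911, which agrees with the stated figure of above 91.0%. An independent calculation (Miettinen-Nurminen restricted variance, one-sided 0.025, margin -10 points, 360/180/540/270 evaluable) gives 99.96%, 99.46% and 91.65%, combined 91.1%. The planned numbers are not in dispute.

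**2. How many people could be affected.** Neither document gives the share drawn on days 43-49. Assume 1% to 5%. Planned evaluable: 360 + 180 + 540 + 270 = 1350, so 14 to 68 people.

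**3. A deliberately severe case for MenB.** Take B24, which has the lowest power in Protocol Table 9 (reference rate 64.5%, 900 versus 450 evaluable). Suppose the true deficit in on-schedule draws is exactly 10 points, and late draws, a share s in both arms, show no arm difference.

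- Observed deficit = 10 × (1 - s): 9.9 points at s = 1%, 9.5 points at s = 5%.
- SE of the difference = √(0.545 × 0.455/900 + 0.645 × 0.355/450) = 2.80 points.
- Shift at s = 5%: 0.5/2.80 = 0.18 SE. The chance of passing is about P(Z > 1.96 - 0.18) = 3.7%.

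Simulation with the score test gives:

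| Late draws show | s = 0 | s = 1% | s = 5% |
|---|---|---|---|
| no arm difference | 2.5% | 2.7% | 3.8% |
| half the arm difference | 2.5% | 2.6% | 3.1% |

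The first row requires up to one extra week before sampling to erase a 10-point deficit completely. The figures are also for one endpoint taken alone. Success requires all 13 primary endpoints to pass (8 ACWY, 5 MenB), so the chance of wrongly declaring overall success cannot exceed the chance for the failing endpoint.

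**4. ACWY, where the arms use different visits.** If late draws lower the response rate by d points, and the late shares are f₁ (MenABCWY, Visit 4) and f₂ (MenACWY-CRM, Visit 2), the shift in the difference is -(f₁ - f₂) × d. With f₁ = 5%, f₂ = 0 and d = 10 (all assumed), it is -0.5 points, which works against noninferiority. Swap the shares and it is +0.5. Nothing in the documents fixes the sign for these eight comparisons.

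**5. Did the evaluable set ever mean full adherence to the schedule?** No.

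- The primary estimands are timed at 1 month after vaccination, without a day range, in participants who meet key protocol criteria.
- The schedule puts Vaccination 2 at 173-194 days, but neither Protocol 9.3 nor SAP section 4 sets a day window for it.
- Protocol 5.2.1.2 delays a blood draw until five full days after systemic antibiotics, so a participant can be sampled late by following the protocol.

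A 28-42 day subset would therefore not be the fully on-schedule population either.

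**6. Was the change permitted, and can a reader see its extent?** Protocol section 9 and SAP section 2 allow the SAP to modify the protocol's plans. They reserve amendments for major changes to primary endpoint definitions or their analysis. SAP section 4 settles population membership before unblinding. SAP 6.5.1 tabulates samples drawn within, before and after the protocol's time frame by randomized group, so the number of late draws in each arm will be reported.

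**The case for a change.** The best case for a change is that it would be cheap and would point in the one direction the plan does not look. mITT is looser still, the subgroup and missing-data analyses do not restrict timing, and SAP 6.5.1 counts late draws without re-estimating any difference. Power does not explain the extension, since Protocol 9.2.1 reaches its target in a document that defines evaluable by 28-42 days. Nor would a restricted repeat be uninformative: with 5% fewer participants in every group the combined power is 89.0%, and with 10% fewer 86.4%, both above the 85% floor in Protocol 9.2.1. The mismatch is not explained by an out-of-date protocol either, because the protocol text already places the secondary MenB strains among the exploratory objectives, as SAP version 3 does.

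Much of this stands. The windows do differ, no reason is given, and a repeat on days 28-42 would do no harm. But the repeat would be supplementary and would leave the primary set, the decision rule and the conclusion as they are. The bias argument rests on a general remark about noncompliance. That remark does not show that a draw up to seven days late narrows the difference between arms. The condition attached to the MenB mITT analysis is a separate question and does not turn on the draw window.

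**Conclusion.** No change to the plan follows. This is a permitted and logged widening that was not carried through to Protocol 9.3 and whose reason was not written down. An analyst following the SAP knows which set to use, and membership is settled without knowledge of vaccine assignment, so there is no sign of outcome-driven selection. Widening by a week keeps more randomized participants in the primary comparison at the price of slightly looser timing, which is a fair trade-off.

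The size is small as far as it can be judged. Under an assumed late share of 1-5%, B24 taken alone at the margin moves from 2.5% to at most 3.8%, and only if late sampling erased the whole arm difference. This is an illustration and not a bound: a larger late share, or late shares that differ between arms, would give other figures. For the eight ACWY comparisons even the direction is unknown. Recording the reason and aligning the wording would be good housekeeping if either document is reissued, but the primary result is sound without it.
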